## **8.3 Final Analyses and Reporting**

Final database lock will occur after all subjects have completed the study assessment period (or withdrew from the study prematurely) and all subject data have been monitored and all queries resolved.

Further exploratory analyses not necessarily identified in this SAP may be performed to support the clinical development program. Any post-hoc or unplanned analyses performed and not described in this SAP will be clearly identified as such in the CSR.

## **8.4 Sample Size**

No formal power calculations were performed to establish the sample size. The number of subjects enrolled who complete the study is historically consistent with other HPA studies.

## **8.5 Subject Disposition**

The number and percent of subjects who were randomized in the study, in each analysis population, who completed the study, who withdrew from the study, and their reasons for withdrawal will be summarized. Subject disposition will be summarized using all subjects who signed informed consent/assent forms and were enrolled in the study.

Subject data listings of the protocol deviations, if any, and analysis population identification will be provided.

## **8.6 Screening and Baseline Assessments**

### **8.6.1 *Demographics***

Demographic information including sex, age, race, and ethnicity will be summarized for the Safety, Evaluable, and PK populations, as well as, screen failures.

### **8.6.2 *Medical History***

Medical history will be provided in a subject data listing for the Safety population.

### **8.6.3 *Physical Examination***

Physical examination abnormalities will not be provided separately, but will be included with medical history.

### **8.6.4 *Vital Signs, Height, and Weight***

Descriptive statistics will be provided for height, weight, temperature, systolic and diastolic blood pressure, heart rate, and respiration rate for the Safety population.

### **8.6.5 *Baseline Clinical Evaluations***

The Screening and Baseline severity scores for IGA will be tabulated for the Safety, Evaluable, and PK populations. The frequency distribution of the body areas affected by plaque psoriasis will be presented. Descriptive statistics will be provided for the Percent BSA Affected and the Percent BSA to be Treated.

### **8.6.6 *Baseline Local Skin Reactions***

The frequency distributions of the Baseline severities of LSRs associated with topical application of corticosteroids including telangiectasia, skin atrophy, burning/stinging, and folliculitis will be summarized for the Safety populations.

## **8.7 Dosing Compliance**

Descriptive statistics will be used to summarize test article compliance for the Evaluable and PK populations. Measures of test article compliance will include the duration of treatment (number of days dosed = last dose date - first dose date + 1), the total number of applications (determined from the actual number of applications reported by the subject), and the percent of expected doses applied. The expected number of doses for subjects who are clear at Day 8 and discontinue from the study is 14. Subjects who continue to Day 15 or early term will have the compliance rate based on an expected 28 doses. A subject will be considered compliant with the dosing regimen if the subject applies at least 80% but no more than 120% of the expected number of applications.

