#### 8.2.2 *Evaluable Population*

The Evaluable population will include those subjects in the Safety population who have both Screening and EOS serum cortisol data (pre- and post-cosyntropin stimulation) and meet the following criteria:

- Meets all inclusion/exclusion criteria, including normal response to cosyntropin stimulation defined as a Screening CST with a 30-minute post-stimulation cortisol level  $>18 \mu\text{g/dL}$ .
- Screening and EOS CST were conducted between 7-9 AM.
- EOS CST was conducted within  $\pm 1$  hour of the Screening CST.
- Applied at least 80% and no more than 120% of the expected number of applications and applied the final dose no more than 14 hours prior to the start of the CST test.

- Has not taken or applied any medications that may interfere with HPA axis function.
- Do not have any other significant protocol deviations.

HPA axis suppression analysis will be conducted on the Evaluable and Safety populations.

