### **8.2.3 *Pharmacokinetic Population***

Subjects included in the PK analysis (PK population) will include those subjects in the Safety population who do not have any significant protocol deviations and must have at least an 80% - 120% dose compliance based on number of applications.

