#### ***8.9.3 HPA Axis Suppression Analyses***

Subjects discontinued from the study at Visit 2 due to abnormal screening laboratory test results or other ineligibility criteria (screen failures) will be excluded from the HPA axis suppression summaries.

The proportion of subjects manifesting laboratory based evidence of adrenal suppression at EOS (as defined in [Section 3.3.1](#)) will be presented along with 95% confidence intervals for the Evaluable and Safety populations. The observed serum cortisol levels (pre-and post-cosyntropin stimulation) and the changes in serum cortisol levels after stimulation at Screening, EOS, and, if any, at follow-up visits will also be summarized. In addition, descriptive statistics for the daily dose of test article will be tabulated separately for suppressed and non-suppressed subjects.

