## **9. CHANGES TO PROTOCOL**

The protocol defined the Safety, modified Intent-to-Treat (mITT), and PK populations. Since an efficacy analysis is not the primary endpoint for this protocol, the mITT population has been replaced with the Evaluable population to be used for the analysis of HPA suppression response. Requirements for inclusion in the Evaluable population are specified so that the CST are consistent between the subjects.

The protocol included the determination of the approximate amount of test article applied per cm^2 prior to the collection of the PK samples at Visit 3 from the estimate of the percent BSA treated with the test article and the amount of test article applied based on the before and after weights of the dose prior to the blood draws. This data was not captured for this study, therefore, this determination will not be performed.

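### SAP 8.7 summarises dosing compliance only in two populations that already require 80-120% compliance, so no compliance summary can include a non-compliant subject

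*SAP*

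**What the plan says.** SAP 8.7 lists three compliance measures: days dosed, number of applications, and percent of expected doses. It names the populations in one sentence: "Descriptive statistics will be used to summarize test article compliance for the Evaluable and PK populations". It calls a subject "compliant with the dosing regimen if the subject applies at least 80% but no more than 120% of the expected number of applications".

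Two denominators are given. For subjects who clear early: "The expected number of doses for subjects who are clear at Day 8 and discontinue from the study is 14". For everyone else: "Subjects who continue to Day 15 or early term will have the compliance rate based on an expected 28 doses".

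Both populations carry the same band as an entry criterion. Evaluable (SAP 8.2.2): "Applied at least 80% and no more than 120% of the expected number of applications". PK (SAP 8.2.3): subjects "must have at least an 80% - 120% dose compliance based on number of applications".

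Protocol 18.3.1 planned the compliance summary for mITT and PK. Under protocol 18.3, mITT needs only one applied dose and one post-baseline visit. SAP Section 9 explains the change: "Since an efficacy analysis is not the primary endpoint for this protocol, the mITT population has been replaced with the Evaluable population". It adds that Evaluable is meant for the suppression analysis and does not mention the compliance summary.

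SAP 3.3.3 lists dosing compliance as a safety endpoint. Under SAP 8.9.3 the suppression proportion "will be presented along with 95% confidence intervals for the Evaluable and Safety populations".

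**The concern.** A compliance summary should show how closely treated subjects followed the regimen, including those who did not. Here the populations are chosen by the quantity being summarised. A subject whom 8.7 would call non-compliant has already been removed from both populations, so the table can describe only variation inside the band.

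Two things are at stake. First, a listed safety endpoint is reported in a form that cannot show non-compliance. Second, suppression is also reported for the Safety population, with no summary beside it of applications, days dosed or percent of expected doses. Protocol 14.3 asks sites to obtain an end-of-study stimulation test from subjects who withdraw early. Under-dosed subjects can therefore contribute to the Safety suppression proportion while appearing in no compliance summary.

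**Working it through.** The plan gives no compliance figure to reproduce. The check compares the rules and then converts the band into whole applications.

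**Rules side by side**

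| Place | Rule on applications |
|---|---|
| SAP 8.7, compliant subject | 80% to 120% of expected |
| SAP 8.2.2, Evaluable | 80% to 120% of expected |
| SAP 8.2.3, PK | 80% to 120% (natural two-sided reading) |
| SAP 8.2.1, Safety | none beyond one application |
| Protocol 18.3, mITT | none beyond one dose and one post-baseline visit |

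The first three coincide, so being non-compliant under 8.7 means being outside both summarised populations.

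**Counts that can appear.** With E expected doses, the lowest count is 0.8 × E rounded up and the highest is 1.2 × E rounded down.

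- E = 14: 0.8 × 14 = 11.2 and 1.2 × 14 = 16.8, so 12 to 16 applications (12/14 = 85.7% to 16/14 = 114.3%).
- E = 28: 0.8 × 28 = 22.4 and 1.2 × 28 = 33.6, so 23 to 33 applications (23/28 = 82.1% to 33/28 = 117.9%).

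**Who is left out**

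- *Early terminators with 22 or fewer applications* (22/28 = 78.6%). With no missed dose, n full days give 2n/28. Stopping after Day 7 gives 14/28 = 50.0% and after Day 11 gives 22/28 = 78.6%, both out. Stopping after Day 12 gives 24/28 = 85.7%, which the band does not exclude.
- *Subjects clear at Day 8 with 11 or fewer, or 17 or more, of 14.* The upper case can arise without misuse. Visit 3 has a window of one day either side, and a cleared subject who must return the next day keeps dosing morning and evening (protocol 10.3). If Visit 3 falls on Day 9 and the end-of-study visit on Day 10, full dosing over Days 1-9 is 18 applications, and 18/14 = 128.6%. Protocol Appendix 1 advises booking Visit 3 on Day 7 or 8, so this should be rare.

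**Size.** Protocol 18.1 expects about 25 enrolled; I assume about 25 treated. Each non-compliant subject is then 1/25 = 4.0 percentage points of the Safety population (1/20 = 5.0 if 20 are treated; 1/30 = 3.3 if 30). For illustration, with k such subjects the Safety proportion compliant is (25 − k)/25: 96%, 92% or 88% for k = 1, 2 or 3. The same proportion in Evaluable or PK would be 100% for every k. The documents give no value for k, and 1 to 3 is not an upper limit.

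**The case against.** The strongest reply is that little information would be lost. Several other outputs partly cover the gap:

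- Grams used are summarised for the Safety population (SAP 8.9.1).
- Daily dose is tabulated for suppressed and non-suppressed subjects (SAP 8.9.3, population not restated for that table).
- Disposition gives counts per population, withdrawals and reasons, with listings of deviations and population membership (SAP 8.5).
- Summary tables are in general backed by listings (SAP 8.1).

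With about 25 subjects, a reader could go through individual records. That stands as mitigation and keeps the point small. It does not close the gap: grams measure exposure rather than adherence to the schedule, and none of these outputs summarises application counts or percent of expected doses in a population that can include non-compliant subjects.

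A second reply is that 8.7 defines a compliant subject but lists no percent-compliant row. That is correct. A reader might infer that the plan will publish a 100% compliance rate; the text does not commit to one. The firm statement is that the listed measures are truncated, and that a percent-compliant figure, if reported, would be 100% by construction.

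Third, the PK wording is awkward. If it were read as a lower limit only, a subject above 120% could enter PK. Under-dosed subjects would still be excluded.

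**Conclusion.** The point holds as a gap in descriptive reporting, and it is minor. On the natural reading of SAP 8.2.3, no planned compliance summary can include a non-compliant subject. The change of population in the SAP removed the one planned summary that could, and Section 9 does not note this. The size is about 4 percentage points of the Safety population per non-compliant subject, assuming about 25 treated; the number of such subjects is unknown.

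Two stronger readings are not supported. A reader might infer that the suppression result is biased by this. It is not: the compliance table does not feed the suppression proportion, which is reported for the Safety population as well as Evaluable. A reader might also infer that everyone who stops early is lost from the table. That is too broad: subjects clear at Day 8 are scored against 14 doses and stay in with 12 to 16 applications, and the band does not exclude early terminators with 23 to 33. Nor should the opposite be assumed, that cleared subjects are always kept, as the 18/14 case shows.

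**What to change.** In the SAP:

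1. In 8.7, summarise compliance for the Safety, Evaluable and PK populations, as 8.9.1 already does for grams used.
2. For the Safety population, report the number and percent of subjects below 80%, within 80-120%, above 120%, and with the application count missing. The missing category is needed because Safety includes treated subjects with no post-baseline visit. Diaries are brought to visits (protocol 6.2.4) and missing values are not imputed (SAP 8.8.2.1), so such subjects may have no count. Without that category the rows may not add up to the population total.
3. In Section 9, record that the protocol's mITT compliance summary is replaced by a Safety summary.

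The cost is one extra table column, one four-category row and a few lines of text. The application counts and dose dates are those 8.7 already uses, and no new data collection is needed. The existing 14- and 28-dose denominators can stay as they are.

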--	---

Product Name: Halobetasol Propionate Lotion, 0.05%

Protocol: 177-0551-201

Sponsor Name: Sun Pharmaceutical Industries, Inc. Protocol Date: August 5, 2016, v3.0

Pharmacokinetic Analysis

Trough HBP concentrations in plasma on Day 8 and Day 15 will be calculated and summarized.

SCHEDE OF EVENTS

Study Day	Visit 1 Screening¹ (-Day 20 or longer)	Visit 2 Day 1 Baseline	Visit 3 Day 8 (± 1)	Optional Visit Day 9	Visit 4 EOS Day 15^{2,3} (± 2) or Early Term
Informed Consent/Assent	X				
Medical History, Demographics, Vital Signs, Height and Weight	X	Reconfirm (except height)			
Limited Physical Exam		X			
Inclusion/Exclusion Criteria	X	Reconfirm			
Urine Pregnancy Test (UPT) ⁴	X	X	X ⁵	X ⁵	X
Cortrosyn® Stimulation Test (CST)	X ⁶	Confirm eligibility ⁶	X ⁷	X ⁷	X ⁷
Percent BSA Affected with Disease	Confirm eligibility	X	X		X
Investigator's Global Assessment (IGA) Score	X	X	X	X ⁵	X ⁵
Percent BSA to be Treated with Test Article	Confirm eligibility	X	X		
Provide (or review) Instruction Sheet to Subject and Demonstrate How to Apply the Test Article		X	X		
Provide Subject Diary to Subject and Completion Instructions		X	X		
Study Treatment (approximately every 12 hours)		X	X ⁵ (withhold AM application until after trough PK blood draw)		
Concomitant Medication Assessments	X	X	X	X ⁵	X
Adverse Events Assessment	X	X	X	X ⁵	X

Study Day	Visit 1 Screening¹ (-Day 20 or longer)	Visit 2 Day 1 Baseline	Visit 3 Day 8 (± 1)	Optional Visit Day 9	Visit 4 EOS Day 15^{2,3} (± 2) or Early Term
Record Local Skin Reactions		X (pre- and post-test article application) ⁹	X (pre- and post-test article application) ⁸	X ⁵	X
Drug Accountability (with Weights)		X	X	X ⁵	X ⁹
PK Blood Draws	X		X (trough approx. 12 hours post-treatment on Day 7)	X ⁵ (trough approx. 12 hours post-treatment on Day 8)	X (trough approx. 12 hours post-treatment; Pre-CST)

1 To be performed 20 or more days prior to the Baseline visit (Day 1).

2 If results at Final Visit show evidence of adrenal suppression, testing will be performed at 4-week intervals until adrenal axis function has normalized or stabilized.

3 Final scheduled visit occurs at Day 15 ± 2.

4 All female subjects will have a UPT at Screening, Baseline and at the end of study

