#### ***8.9.4 Pharmacokinetic Analyses***

Morning trough concentrations of HBP in plasma at Screening, Day 8 and Day 15 will be summarized for the PK population using geometric mean, coefficient of variation in addition to n, mean, median, standard deviation, minimum and maximum.

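### SAP 8.7 scores compliance against a fixed 14 or 28 doses whatever the visit day, so a fully adherent early terminator's Day 8 trough drops out of the only PK summary

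*SAP*

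**What the plan says.** SAP 8.7 gives two denominators for the compliance rate. For early clearers: "The expected number of doses for subjects who are clear at Day 8 and discontinue from the study is 14". For the rest: "Subjects who continue to Day 15 or early term will have the compliance rate based on an expected 28 doses". Neither document defines expected applications in any other way, and nothing adjusts the count for the day on which the visit took place.

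The score gates two populations. SAP 8.2.2 admits a subject to the Evaluable population who "Applied at least 80% and no more than 120% of the expected number of applications" and who also "applied the final dose no more than 14 hours prior to the start of the CST test". SAP 8.2.3 says PK subjects "must have at least an 80% - 120% dose compliance based on number of applications". It sets no completion criterion and no limit on time since the last dose.

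The outputs differ in how far they depend on the gate. SAP 8.9.4: "Morning trough concentrations of HBP in plasma at Screening, Day 8 and Day 15 will be summarized for the PK population". No other population is named for the troughs. SAP 8.9.3 says the suppression proportion "will be presented along with 95% confidence intervals for the Evaluable and Safety populations".

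Visit days vary by design. Protocol 10.3 allows Visit 3 on Day 8 ± 1, and Appendix 1 advises sites to use Day 7 or 8. For Visit 4, the Schedule of Events (footnote 3) says: "Final scheduled visit occurs at Day 15 ± 2".

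**The concern.** Dosing stops the evening before the visit, so the number of doses a subject could have applied depends on the visit date. The SAP's denominator does not. Two things follow.

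First, an early terminator is measured against a two-week course even for a sample drawn after one week. Withdrawal after Visit 3 says nothing about dosing before the Day 8 draw, yet it can remove that trough from the summary. PK is half of the study objective and only about 25 subjects are to be enrolled. The loss may also be selective, since Protocol 14.2 lists adverse events and worsening among the reasons for withdrawal.

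Second, for subjects who finish on an early but permitted day, the number of missed doses that the gate forgives depends on the calendar.

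**Working it through.** **Inputs.** Two applications on Day 1, then twice daily (Protocol 10.2). Morning application withheld on the visit day until the draw (Protocol 10.2, 10.3). Visit windows Day 7-9 and Day 13-17. Denominators 14 and 28 and the 80-120% band (SAP 8.7).

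**Reproducing the plan's figures.** Doses due before the visit = 2 × (visit day − 1). Day 8: 2 × 7 = 14. Day 15: 2 × 14 = 28. Both SAP counts are exact on the nominal days.

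**Whole-dose limits.** 0.8 × 14 = 11.2 and 1.2 × 14 = 16.8, so 12 to 16 applications pass. 0.8 × 28 = 22.4 and 1.2 × 28 = 33.6, so 23 to 33 pass.

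**1. Early termination with no dose missed (denominator 28).**

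| Visit day | Morning dose withheld | Morning dose applied |
|---|---|---|
| 8 | 14/28 = 50.0% | 15/28 = 53.6% |
| 9 | 16/28 = 57.1% | 17/28 = 60.7% |
| 10 | 18/28 = 64.3% | 19/28 = 67.9% |
| 11 | 20/28 = 71.4% | 21/28 = 75.0% |
| 12 | 22/28 = 78.6% | 23/28 = 82.1% (passes) |
| 13 | 24/28 = 85.7% (passes) | 25/28 = 89.3% (passes) |

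Days 8-11 fail either way, and Day 12 fails only if the morning dose was withheld. A subject clear on Day 8 with the same 14 applications scores 14/14 = 100%.

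**2. In-window visits, missed doses tolerated.**

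| Visit day | Doses due | Needed under 8.7 | Misses tolerated | 80% of doses due | Misses tolerated |
|---|---|---|---|---|---|
| 7 (clear) | 12 | 12 | 0 | 9.6, so 10 | 2 |
| 8 (clear) | 14 | 12 | 2 | 11.2, so 12 | 2 |
| 13 | 24 | 23 | 1 | 19.2, so 20 | 4 |
| 14 | 26 | 23 | 3 | 20.8, so 21 | 5 |
| 15 | 28 | 23 | 5 | 22.4, so 23 | 5 |

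Examples: 11 of 12 at Day 7 is 91.7% of doses due but 11/14 = 78.6% under the SAP. At Day 13, 22 of 24 is 91.7% but 22/28 = 78.6%. With nothing missed, Day 7 gives 12/14 = 85.7% and Day 13 gives 24/28 = 85.7%, and both pass.

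**Illustration only.** The documents give no rate of missed doses. Assume independent misses at 2%, 5% or 10% per dose and a visit on the stated day. The binomial chance of failing SAP 8.7 while meeting 80% of doses due is then 21%, 44%, 61% at Day 7; 8%, 33%, 62% at Day 13; and 0.2%, 4%, 22% at Day 14. For Day 7 at 5%: 12 × 0.05 × 0.95^11 + 66 × 0.05² × 0.95^10 = 0.341 + 0.099 = 0.44.

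**3. Effect on the suppression proportion.** Assume 5 of 20 suppressed (25.0%; Protocol section 1 reports 23.8% for the lotion in adults). Losing one non-suppressed subject gives 5/19 = 26.3%, and losing one suppressed subject gives 4/19 = 21.1%. The exact 95% interval for 5/20 is 8.7% to 49.1%.

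**The case against.** The best defence is that 28 is a deliberate choice. The planned course is two weeks, and scoring against it holds continuing subjects to at least 23 applications in a study of adrenal suppression. A denominator based on doses due would admit Day 13 completers with 20 applications, or 20/28 = 71.4% of the planned course, and lower exposure could understate suppression. Protocol 18.1 also counts only subjects who completed the study as evaluable. This stands for the Evaluable population, and the fix has to allow for it. It does not justify dropping a Day 8 trough, because the PK population has no completion criterion and later withdrawal cannot change exposure before the draw.

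A second objection also stands: the 28-dose base does some useful work. The Schedule of Events places a PK draw at early termination, and PK entry has no time-since-dose limit. Simply relaxing the denominator could let a sample taken days after the last application into the Day 15 summary.

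Four stronger readings are tempting, and the documents do not support them:

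- *Every early terminator on Day 8-12 loses a valid trough.* The loss requires a Visit 3 sample and sound prior dosing, and Day 12 can pass. The value is lost from the summary; SAP 8.1 says tables are in general backed by subject listings.
- *Fully adherent subjects fail at early scheduled visits.* They do not. Some doses must also have been missed, and the Day 7 case applies only to subjects who are clear at that visit.
- *A Day 9 finisher with 12 applications is wrongly kept.* Protocol 10.3 footnote 8 has morning and evening dosing on Day 8 (16 due; 12/16 = 75.0%). Protocol 10.4 mentions only the evening (15 due; 12/15 = 80.0%). The two passages must be reconciled first.
- *Day 16-17 visits are scored too leniently.* This depends on whether dosing runs past Day 14. Protocol 6.2.1 puts the final application on Day 14, whereas 10.3 ties it to the evening before the visit. These too must be reconciled.

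**Conclusion.** The point holds and is minor. The main defect is that a fully adherent early terminator seen on Day 8-11 (or Day 12 with the morning dose withheld) fails the PK gate at 50.0-71.4% (or 78.6%), so a valid Day 8 trough appears in no PK summary. The lesser defect is the calendar-dependent tolerance at Day 7, 13 and 14. The rule is exact at Day 8 and Day 15.

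The conclusion assumes that SAP 8.7 supplies the compliance rate used in 8.2.3. That section does not cite it, but no other definition exists. It also assumes that withdrawal is not in itself a significant protocol deviation, which the SAP does not say it is. How many subjects are affected cannot be worked out from the documents. A reader might infer that the suppression result is materially biased. That is not supported: the proportion is also reported with an interval in the Safety population, and a shift of one subject is small against the interval's width.

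**What to change.** 1. **Day 8 trough summary.** Compute compliance as applications from first dose to the Day 8 draw over doses due in that interval, so that later withdrawal does not remove the sample.
2. **PK gate at end of study.** Use doses due to the actual visit date. Include an end-of-study or early-termination sample in the Day 15 trough summary only if it was drawn about 12 hours after the last recorded application, the timing that SAP 7.2 describes.
3. **Evaluable gate.** Use doses due to the actual visit date for subjects who completed the study as SAP 5 defines it, and state completion as a criterion in 8.2.2. Otherwise early terminators, for whom Protocol 14.3 asks for an end-of-study CST, could enter as 100% compliant.
4. **Sensitivity.** Also show the suppression proportion under the present 8.7 denominators.
5. **Record.** List the change in SAP 9 and settle it before database lock, without reference to cortisol or trough results, because the study is open label. Reconcile the Day 9 and Day 16-17 dosing passages before coding doses due.

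**Cost.** Wording in SAP 8.2.2, 8.2.3, 8.7, 8.9.3, 8.9.4 and 9, plus derived variables from visit dates, diary counts and the last-application time already collected (Protocol 6.2.4 and Appendix 3, A 3.6). The number of subjects may differ between the Day 8 and Day 15 PK summaries. Some Day 13-14 completers with as few as 20-21 applications would enter the Evaluable population, which is why item 4 is needed.
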